8.1 Primary Objective

The primary objective of this study is to compare rhFSH-alfa reference product with HP-hMG or rhFSH-alfa biosimilar products regarding the following live birth outcome measures:

- a) LBR per initiated IVF/ICSI stimulation cycle
- b) CLBR per initiated IVF/ICSI stimulation cycle
- c) CLBR in up to five initiated IVF/ICSI stimulation cycles [termed multiple-cycle (MC-)CLBR]

8.2 Secondary Objectives

There are multiple secondary objectives, where secondary objectives 1-4 examine treatment effectiveness and secondary objectives 5-8 treatment safety. Hence, the secondary objectives compare rhFSH-alfa reference product with HP-hMG or rhFSH-alfa biosimilar products regarding the following outcomes:

1. a) CPR and OPR per initiated IVF/ICSI stimulation cycle, and b) cumulative clinical pregnancy rate (CCPR) and COPR per initiated IVF/ICSI stimulation cycle

2. Number of oocytes retrieved, embryos transferred, embryos cryopreserved, and utilizable embryos per initiated IVF/ICSI stimulation cycle and per oocyte retrieval cycle
3. Implantation rate
4. TTLB
5. Rate of pregnancy loss for the first (and successive) IVF/ICSI stimulation cycle(s)
6. Rate of multiple pregnancy for the first (and successive) IVF/ICSI stimulation cycle(s)
7. Number of cancelled cycles for the first (and successive) IVF/ICSI stimulation cycle(s)
8. Number of OHSS cases for the first (and successive) IVF/ICSI stimulation cycle(s)

An additional secondary objective describes treatment-associated costs. Hence, the secondary objective 9 is to describe the following outcomes for the rhFSH-alfa reference product, HP-hMG and rhFSH-alfa biosimilar products individually and overall, across all products:

9. Costs associated with IVF/ICSI treatment (including drugs and other treatments), miscarriage/birth, and adverse events (i.e., OHSS)

9 Research Method

9.1 Study Design

9.1.1 Design Overview

This is a non-interventional study based on secondary data from national population-based registers in Denmark and Sweden. The study uses a cohort design and is conducted as a comparative effectiveness and safety study with head-to-head comparisons of drugs used for treatment of infertility and in ART. The study drugs are rhFSH-alfa reference product (drug of interest), HP-hMG and rhFSH-alfa biosimilar products (comparator drugs). Together with the rhFSH-alfa reference product, the comparator drugs constitute the main gonadotropins used for COS in ART in both countries of study in recent years. In 2019, the three study drugs comprised 96% of all dispensed prescriptions for gonadotropins in Sweden. In Denmark, the study drugs comprised 89% of all volume sales in the same year¹. Comparisons will be made between the rhFSH-alfa reference product and each comparator drug with respect to clinical effectiveness and safety. Treatment-associated costs will be described. Thus, the newer generation rhFSH-alfa reference product will be evaluated both against the older generation products, HP-hMG, and the newest generation rhFSH-alfa products, the biosimilars.

¹ Publicly available information from each country's online statistical database on pharmaceuticals (*Denmark*: <https://medstat.dk/en>; *Sweden*: https://sdb.socialstyrelsen.se/if_lak/val_eng.aspx). The following ATC codes were used in the search for statistics on sales volumes and number of dispensed prescriptions: G03GA02 (hMG), G03GA04 (urofollitropin), G03GA05 (follitropin alfa), G03GA06 (follitropin beta), G03GA09 (corifollitropin alfa), G03GA30 (combinations). Accessed 10 February 2021.

Data will be obtained from nationwide, electronically recorded, population-based registers with prospective data collection. In particular, the IVF register in each country will be used to establish the study population. The IVF registers hold comprehensive information on ART treatments conducted at all fertility clinics, publicly- and privately-operated, in Denmark and Sweden, respectively. The study will therefore enable inclusion of information on IVF treatments among the entire female population of each country. The unique personal identification number assigned to individuals at birth or immigration in each country further allows for linkage of individual-level data across multiple registers and subsequently the creation of country-specific customized study databases. Data will be obtained on IVF/ICSI treatment characteristics, dispensed prescription drugs (including exposure to the study drugs, GnRH protocol used, etc.), pregnancy and other treatment outcomes, medical history, laboratory test results (Denmark only), and costs. The contents, set-up and structure of each national register is similar across the two countries, including coding classification systems such as the International Classification of Diseases, 10th revision (ICD-10) and the Anatomical Therapeutic Chemical (ATC) classification system. The same type of analyses can therefore be performed in both countries, with little need for adaptation. Individual-level data will be analyzed separately for each country. Meta-analysis may be used, as appropriate, to provide summary estimates for the entire study population across both countries.

[figure not shown]
The study will include IVF or ICSI stimulation cycles and the FET cycles linked to the same stimulation cycles among women who received rhFSH-alfa reference product, HP-hMG or rhFSH-alfa biosimilar products for COS (Figure 1). The overall qualifying event for study inclusion will thus be a recorded IVF/ICSI stimulation cycle with one of the study drugs. Three study cohorts will be created, including stimulation cycles with rhFSH-alfa reference product, HP-hMG, and rhFSH-alfa biosimilar products, respectively. Women may contribute cycles to more than one study cohort. Any linked FET cycles will be assigned to the same cohort as the stimulation cycle it originated from. The study will be restricted to the first five stimulation cycles observed in each woman in the IVF registers, regardless if they occurred in the study period and the gonadotropin (study drug or non-study drug) used for COS. The study is restricted to the first five stimulation cycles as it is known that the CLBR per cycle decreases over the first five cycles and is maintained at a similarly low level beyond the fifth stimulation cycle and the number of women continuing treatment diminishes substantially with each advancing cycle number (20,21). Further, the study population will be restricted to women who, on the day of treatment initiation (ovarian stimulation start) and 3 years prior, resided in the country where the treatment was performed. This will allow for a minimum baseline period of 3 years during which any previous IVF/ICSI treatment and information on potential confounders can be assessed.

The overall study period will be between 2010 and 2020. Different study period starts will be applied depending on which two drugs are being compared. For the comparison between rhFSH-alfa reference product and HP-hMG, the study period will start 1 January 2010 for both countries. This date is selected to ensure the study is sufficiently powered while also reducing heterogeneity in patient management over time. Changes that have occurred over time include moving towards vitrification rather than slow freezing for embryo cryopreservation and hence also moving from cleavage stage to blastocyst embryo transfers, elective single embryo transfers rather than double embryo transfers, and antagonist protocols rather than agonist protocols. For the comparison between rhFSH-alfa reference product and rhFSH-alfa biosimilar products, the study period will start 26 March 2014 for Denmark and 20 June 2014 for Sweden. These are the earliest dates when a rhFSH-alfa biosimilar product (Bemfola) received reimbursement status in each country. For

Sweden, where the IVF register is updated annually and has a lag time of approximately two years (see Section 9.4.2), inclusion of women undergoing IVF/ICSI treatment may end on 31 December 2019, depending on data availability at the time of data extraction. No such general restriction will be applied for Denmark, as the IVF register is updated monthly. In terms of follow-up of IVF/ICSI treatment and pregnancy outcomes, the study will end on 31 December 2020 (or last available date) for each country. Specifically, for the main analyses of the primary objective (LBR, CLBR and MC-CLBR) and secondary objective 4 (TTLB), a minimum follow-up period of 1 year has been chosen to allow sufficient time to achieve (at least) one live birth and a reasonable number of complete cycles for reliable estimates of live birth rates. Hence, the corresponding analyses are restricted to cycles initiated on or before 31 December 2019 (Sets 1 and 5 in Table 5). The minimum follow-up period will be extended to 2 years in a sensitivity analysis to explore the potential effect this has on the estimated MC-CLBR and TTLB (see sensitivity analysis 3 in Table 8).

To reduce possible bias linked to confounding by baseline characteristics, inverse probability of treatment weighting (IPTW), based on propensity scores (PS) (22), will be used to balance the distribution of potential confounders across the study cohorts.

Figure 1. Study design

BMI: body mass index; COS: controlled ovarian stimulation; GnRH: gonadotropin-releasing hormone; HP-hMG: highly purified human menopausal gonadotropin; ICSI: intracytoplasmic sperm injection; IVF: in vitro fertilization; LPS: luteal phase support; PCOS: polycystic ovarian syndrome; rhFSH: recombinant human follicle-stimulating hormone.

9.1.2 Outcomes

The primary and secondary outcomes detailed below will be identified using linked data from the IVF registers, patient registers and medical birth registers in Denmark and Sweden, as needed. An overview of how the registers will be used for outcome identification is provided in Appendix 3

(Section 14.3.1), along with diagnosis and procedure codes to ascertain the outcomes (where applicable).

9.1.2.1 Primary

The primary outcome of this study is live birth. It is defined generally as the complete expulsion or extraction from a woman of a product of fertilization, after 22 completed weeks of gestational age; which, after such separation, breathes or shows any other evidence of life, such as heartbeat, umbilical cord pulsation or definite movement of voluntary muscles, irrespective of whether the umbilical cord has been cut or the placenta still attached or not (16).

Information on live birth will be obtained from the medical birth register in each country and the IVF register in Sweden. Only live births that can be linked to a given IVF/ICSI stimulation cycle included in the study will be considered. The live birth of multiples will be counted as one live birth in this study.

For the assessment of the primary objective and secondary objective 4, the different measures of live birth are defined as follows:

- LBR is the probability of a live birth after one initiated stimulation cycle, considering fresh embryo transfer.
- CLBR is the number of live births per initiated stimulation cycle, considering all fresh and subsequent frozen embryo transfers linked to that stimulation cycle and counting all live births from the same transfers.
- MC-CLBR is the probability of a live birth in up to five stimulation cycles, considering all fresh and subsequent frozen embryo transfers linked to each of those stimulation cycles, until the first live birth occurs.
- TTLB is the time (in number of cycles) until live birth in up to five stimulation cycles, considering all fresh and subsequent frozen embryo transfers linked to each of those stimulation cycles, until the first live birth occurs.

For the calculation of the above measures, refer to Section 9.7.3.3 (Table 7).

9.1.2.2 Secondary

There are several secondary outcomes, which are connected to the secondary study objectives:

1. Clinical pregnancy is defined generally as pregnancy diagnosed by ultrasonographic visualization of one or more gestational sacs. It includes intrauterine pregnancy and clinically documented ectopic pregnancy (16). In this study, multiple embryos will be counted as one clinical pregnancy.

Intrauterine pregnancy will be ascertained in the IVF registers. Diagnosis and procedure codes used to ascertain ectopic pregnancy in the national patient registers are provided in Appendix 3 (Section 14.3.1).

For the assessment of secondary objective 1, clinical pregnancy is measured as CPR and CCPR, which are defined analogously to LBR and CLBR:

- CPR is the probability of a clinical pregnancy after one initiated stimulation cycle, considering fresh embryo transfer.
 - CCPR is the number of clinical pregnancies per initiated stimulation cycle, considering all fresh and frozen embryo transfers lined to that stimulation cycle and counting all clinical pregnancies from the same transfers.
2. Ongoing pregnancy is defined in this study as pregnancy still ongoing at 22 completed weeks of gestational age. It will be ascertained based on a record of miscarriage or induced abortion (before 22 completed weeks of gestational age), or gestational age at delivery in the national patient registers or the IVF register in Sweden. Multiples will be counted as one ongoing pregnancy.

For the assessment of secondary objective 1, ongoing pregnancy is measured as OPR and COPR, which are defined analogously to LBR and CLBR:

- OPR is the probability of an ongoing pregnancy after one initiated stimulation cycle, considering fresh embryo transfer.
- COPR is the number of ongoing pregnancies per initiated stimulation cycle, considering all fresh and frozen embryo transfers linked to that stimulation cycle and counting all ongoing pregnancies from the same transfers.

Only clinical pregnancies and ongoing pregnancies that can be linked to a given IVF/ICSI stimulation cycle included in the study will be considered.

3. Oocytes retrieved is defined generally as the total number of oocytes retrieved from an ovarian follicular aspiration following COS. Information on the number of oocytes retrieved will be ascertained in the IVF registers.
4. Embryos transferred is defined generally as the total number of embryos placed into the uterus following IVF or ICSI. Information on the number of embryos transferred will be ascertained in the IVF registers. This outcome is applicable to both fresh and frozen embryo transfers.
5. Embryos cryopreserved is defined generally as the total number of embryos cryopreserved following COS, follicular aspiration, and embryo cultivation, using the process of slow freezing or vitrification to preserve cleavage-stage embryos. Information on the number of embryos cryopreserved will be ascertained in the IVF registers.
6. Utilizable embryos are defined as the sum of number embryos transferred and number embryos cryopreserved.
7. Implantation is defined generally as the attachment and subsequent penetration by a zona-free blastocyst into the endometrium. This process starts 5 to 7 days after fertilization of the oocyte usually resulting in the formation of a gestation sac (16). It will be ascertained in the IVF registers based on ultrasonographic visualization of the number of gestational sacs.

8. Pregnancy loss is defined generally as the miscarriage or induced abortion of an intrauterine pregnancy before 22 completed weeks of gestational age. Diagnosis and procedure codes used to ascertain pregnancy loss are provided in Appendix 3 (Section 14.3.1). Only complete pregnancy losses, *i.e.*, involving all fetuses in case of multiple pregnancy, will be considered.
9. Multiple pregnancy is defined generally as a pregnancy with more than one embryo or fetus. It will be ascertained in this study based on ultrasonographic visualization of two or more gestational sacs and information on pregnancy outcome, to account for cases of monozygotic twins. Because monozygotic twins share the same gestational sac, an algorithm will be developed which considers data on intrauterine pregnancy loss and data on live or stillbirth. In this way, reduction of multiple pregnancy is accounted for, which is particularly important for Denmark as the Danish In-Vitro Fertilization Register (DIVF) does not record pregnancy outcome. The algorithm will be detailed in the statistical analysis plan (SAP).
10. Cycle cancellation is defined generally as a cycle in which ovarian stimulation or monitoring has been initiated with the intention to treat, but which did not proceed to follicular aspiration or, in the case of a thawed or warmed embryo, did not proceed to embryo transfer. Information on cycle cancellation will be ascertained in the IVF registers.
11. Ovarian hyperstimulation syndrome is defined generally as an exaggerated systemic response to COS characterized by a wide spectrum of clinical and laboratory manifestations. It will be ascertained in this study based on a recorded primary or secondary diagnosis of OHSS within inpatient or outpatient specialized care within 70 days (10 weeks) after oocyte retrieval or as recorded in the IVF registers in a given IVF/ICSI stimulation cycle. For descriptive purposes, OHSS will be classified as early if it occurred within 9 days after oocyte retrieval, and late if it occurred 10 or more days after oocyte retrieval. The day of hospital admission (inpatient care) or hospital visit (outpatient care) will be defined as the onset of OHSS (23). A woman may experience both early and late OHSS. Thus, for the description of OHSS, a woman may be counted towards the early and late classification in a given cycle. For the combined measure to be used in the comparative analyses, only one occurrence of OHSS per cycle will be counted. If a new cycle was initiated within 70 days after oocyte retrieval, the previous stimulation cycle will be excluded from further descriptive and comparative analyses with respect to OHSS from the date of treatment start for the new cycle. The diagnosis code used to ascertain OHSS is provided in Appendix 3 (Section 14.3.1).
12. Treatment-associated costs are defined as direct medical costs of treatments (drugs and other treatments), pregnancy loss/birth, and adverse events (*i.e.*, OHSS) resulting from an IVF/ICSI stimulation cycle.

Detailed definitions for ascertainment of the secondary outcomes using ICD-10 and procedure codes, as applicable, are provided in Appendix 3 (Section 14.3.1). For the calculation of the secondary outcome measures, refer to Section 9.7.3.3 (Table 7).

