Secondary objective 1	CPR	Number of clinical pregnancies after fresh embryo transfer	Initiated cycles with drug of interest
	CCPR	Number of clinical pregnancies after one initiated stimulation cycle, including all fresh or frozen embryo transfers linked to that cycle	Initiated cycles with drug of interest
	OPR	Number of ongoing pregnancies after fresh embryo transfer	Initiated cycles with drug of interest
	COPR	Number of ongoing pregnancies after one initiated stimulation cycle, including all fresh or frozen embryo transfers linked to that cycle	Initiated cycles with drug of interest
Secondary objective 2	Number of oocytes retrieved	Number of oocytes retrieved	Initiated cycles with drug of interest
		Number of oocytes retrieved	Aspirated cycles with drug of interest

Study objective	Outcome measure	Numerator	Denominator
	Number of embryos transferred	Number of fresh embryos transferred	Fresh embryo transfers linked to cycles with drug of interest
		Number of frozen embryos transferred	Frozen embryo transfers linked to cycles with drug of interest
	Number of embryos cryopreserved	Number of embryos cryopreserved	Initiated cycles with drug of interest
		Number of embryos cryopreserved	Aspirated cycles with drug of interest
	Number of utilizable embryos	Number of utilizable embryos	Initiated cycles with drug of interest
		Number of utilizable embryos	Aspirated cycles with drug of interest
Secondary objective 3	Implantation rate	Number of intrauterine gestational sacs after one fresh or frozen embryo transfer	Number of embryos transferred in one cycle
Secondary objective 4	TTLB	Time to first delivery with at least one live birth in up to five stimulation cycles with the same study drug, including all fresh or frozen embryo transfers linked to each of those stimulation cycles	N/A; conducted as time-to-event analysis; unit of analysis is women who initiated stimulation cycles with drug of interest
Secondary objective 5	Rate of pregnancy loss	Number of induced and spontaneous abortions	Clinical pregnancies with drug of interest following fresh or frozen embryo transfer
Secondary objective 6	Multiple pregnancy rate	Number of multiple pregnancies	Clinical pregnancies with drug of interest following fresh or

Study objective	Outcome measure	Numerator	Denominator
			frozen embryo transfer
Secondary objective 7	Cycle cancellation rate	Number of canceled cycles	Initiated cycles with drug of interest, including any linked initiated FET cycles

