9.7.3.4 Adjusted Odds Ratios

For the comparison of the study cohorts, the ORs (with 95% CI), adjusted for confounding factors, will be estimated by taking into account the IPTWs and using statistical modelling, such as regression analysis or general estimating equations. To estimate the adjusted ORs, the statistical model will be weighted with IPTWs and will include as covariates any variables that were used in the PS but are still unbalanced between the study cohorts after weighting. Statistical models may also be used to additionally adjust the ORs for any other potential covariates that are assessed after the initiation of the IVF/ICSI stimulation cycle and hypothesized to be associated with the given study outcomes (see Table 1 in Section 9.3.2).

For the statistical models, the following study outcomes will be considered as binary outcomes analyzed per fresh embryo transfer: live birth (*i.e.*, a primary objective outcome), clinical pregnancy and ongoing pregnancy (*i.e.*, a subset of secondary objective 1 outcomes). For the statistical models, the following study outcomes will be considered as binary outcomes analyzed per woman: MC-CLBR (*i.e.*, a primary objective outcome) will be analyzed as a binary outcome per woman in statistical models.

For the statistical models, the following study outcomes will be considered as binary outcomes analyzed per clinical pregnancies following fresh or frozen embryo transfer: pregnancy loss (secondary objective 5) and multiple pregnancy (secondary objective 6). Cycle cancellation (secondary objective 7) and OHSS occurrence (secondary objective 8) will be analyzed as binary outcomes per initiated stimulation cycle. Implantation (secondary objective 3) will be analyzed as an ordinal categorical outcome per fresh or frozen embryo transfer.

For the statistical models, the following study outcomes are considered as counts analyzed per initiated stimulation cycle: cumulative live birth (*i.e.*, a primary objective outcome), cumulative clinical pregnancy and cumulative ongoing clinical pregnancy (*i.e.*, a subset of secondary objective 1 outcomes). Also the following study outcomes are considered as counts in statistical models and

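### The pregnancy-loss rate counts only intrauterine losses but divides by all clinical pregnancies, so an ectopic pregnancy is scored as not lost

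*Protocol*

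**What the plan says.** Section 9.1.2.2 of the Protocol (item 1) says of clinical pregnancy: "It includes intrauterine pregnancy and clinically documented ectopic pregnancy (16". Ectopic pregnancies are actively sought: "Diagnosis and procedure codes used to ascertain ectopic pregnancy in the national patient registers are provided in Appendix 3". Section 14.3.1 lists O00, MCB 00, LAA 20 and LBC* for this purpose. The intrauterine component is ascertained separately, in the IVF registers.

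Item 8 of the same section limits pregnancy loss to "the miscarriage or induced abortion of an intrauterine pregnancy before 22 completed weeks of gestational age". The codes in Section 14.3.1 are O03 to O06 and LCH*; O00 is not among them.

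Table 7 (Section 9.7.3.3) gives the numerator of the loss rate as "Number of induced and spontaneous abortions" and the denominator as "Clinical pregnancies with drug of interest following fresh or frozen embryo transfer". Table 6 names the same unit, the clinical pregnancy. Section 9.7.3.4 carries it into the regression models: "binary outcomes analyzed per clinical pregnancies following fresh or frozen embryo transfer: pregnancy loss (secondary objective 5) and multiple pregnancy (secondary objective 6". None of these places restricts the pregnancies to intrauterine ones.

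Section 8.2 classes objectives 5 to 8 as safety objectives.

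**The concern.** A rate should have a numerator drawn from the pregnancies in its denominator that could have had the event. Under these definitions a pure ectopic pregnancy is in the denominator but can never be in the numerator. In the binary model for objective 5 it is a zero, the same value as a pregnancy that continued.

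An unfavourable pregnancy outcome therefore lowers the reported loss rate. If the share of ectopic pregnancies differed between cohorts, the cohort with more of them would show an odds ratio shifted towards fewer losses, even with identical intrauterine loss risk. Section 8 hypothesizes superiority in safety as well as effectiveness, so the loss comparison should not depend on how many ectopic pregnancies each cohort contains. Weighting by the propensity score does not remove this, because it balances baseline covariates and does not alter the outcome definition.

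**Working it through.** The Protocol states no loss rate and no ectopic rate, so there is no figure of its own to reproduce. The first step compares definitions; the second is illustrative arithmetic on assumed inputs.

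**Definitions side by side (objective 5)**

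| Element | Source | Intrauterine | Ectopic |
|---|---|---|---|
| Clinical pregnancy | 9.1.2.2 item 1; 14.3.1 | included | included (O00, MCB 00, LAA 20, LBC*) |
| Pregnancy loss | 9.1.2.2 item 8; 14.3.1 | included (O03 to O06, LCH*) | excluded |
| Rate denominator | Table 7 | included | included |
| Model unit | Table 6; 9.7.3.4 | included | included |

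The one exception is a pregnancy with both an intrauterine and an ectopic part in which the intrauterine part is lost. This is negligible, and the statements here concern pure ectopic pregnancies.

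**Formulas**

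Let L be the loss risk per intrauterine pregnancy and e the ectopic share of clinical pregnancies.

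- Rate as the Protocol defines it: L(1 − e)
- Rate with an intrauterine denominator: L
- Odds ratio of cohort B to cohort A: [b/(1 − b)] / [a/(1 − a)], where a and b are the two rates

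**Assumed inputs:** L = 20% (range 15% to 25%), the same in both cohorts; e = 1% to 5%.

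**Dilution of the rate at L = 20%**

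- e = 1%: 0.20 × 0.99 = 19.8%
- e = 4%: 0.20 × 0.96 = 19.2%
- e = 5%: 0.20 × 0.95 = 19.0%

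**Odds ratio at L = 20%, with no true difference in intrauterine loss**

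| e in A | e in B | Rate A | Rate B | OR (B/A) as defined | OR, intrauterine denominator |
|---|---|---|---|---|---|
| 1% | 1% | 19.8% | 19.8% | 1.00 | 1.00 |
| 1% | 2% | 19.8% | 19.6% | 0.99 | 1.00 |
| 1% | 3% | 19.8% | 19.4% | 0.97 | 1.00 |
| 1% | 4% | 19.8% | 19.2% | 0.96 | 1.00 |
| 2% | 5% | 19.6% | 19.0% | 0.96 | 1.00 |
| 1% | 5% | 19.8% | 19.0% | 0.95 | 1.00 |

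For 4% against 1%: (0.192/0.808) / (0.198/0.802) = 0.2376/0.2469 = 0.96. For the other unequal pairs in the table, varying L from 15% to 25% leaves the odds ratios within about 0.95 to 0.99.

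**The case against.** **The distortion is conditional and small.** The odds ratio moves only if ectopic shares differ, and the Protocol gives no ectopic rate and no reason to expect a difference by gonadotropin. This stands. A reader might infer that the plan favours one product, or the reference product in particular. The document does not support that.

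**It would probably lie within sampling error.** Take the Danish cycle counts for the HP-hMG comparison in Table 2 (53,000 and 33,000) and apply to cycles the 75% eligibility that Section 9.5 states for women. This gives 39,750 and 24,750 cycles. Assume 25% to 40% of cycles yield a clinical pregnancy, 20% loss, and no clustering or weighting. The half-width of the 95% interval for the log odds ratio is 1.96 × √[1/(n₁ × 0.16) + 1/(n₂ × 0.16)].

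- At 25% (9,938 and 6,188 pregnancies) it is 0.08.
- At 40% (15,900 and 9,900) it is 0.06.
- For the Danish biosimilar comparison (31,000 and 5,000 cycles) at 30% (6,975 and 1,125 pregnancies) it is 0.16.

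The shift at 4% against 1% is ln(0.96) ≈ −0.04. This also stands as a limit on size. It does not make the definition right, and the mismatch is systematic where sampling error is not.

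**Multiple pregnancy.** A reader might extend the point to objective 6, which has the same denominator. The documents do not show a mismatch there. Section 9.1.2.2 item 9 defines multiple pregnancy by the number of embryos or fetuses, without restriction to intrauterine pregnancies, and leaves the detailed algorithm to the SAP.

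**CPR and CCPR.** A reader might also object that an ectopic pregnancy counts towards these rates. That follows the cited definition and is not an error. The live-birth measures are unaffected, since they require a live birth.

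**The SAP.** Section 9.7.1 leaves modifications of the analysis sets to the SAP, and Section 14.3 allows code lists to be revised. The SAP was not available, and a restriction could be made there. But the Protocol itself fixes the numerator, denominator, codes and model unit for pregnancy loss, and neither provision removes that rule.

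**Conclusion.** The point holds for pregnancy loss (secondary objective 5). Followed as written, the plan scores every pure ectopic pregnancy as a pregnancy not lost and reports L(1 − e) where the loss definition calls for L. That much follows from the text alone.

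The size rests on assumptions. With L = 20% and e between 1% and 5%, the absolute rate is understated by 0.2 to 1.0 percentage points. The odds ratio stays at 1.00 if ectopic shares are equal and is roughly 0.95 to 0.99 for the cohort with more ectopic pregnancies under the unequal shares tried. The direction relative to the ectopic share is fixed, but which product would benefit is unknown. No primary outcome is affected. It is a definitional correction to one safety rate, worth making because it is cheap, and does not show that a conclusion of the study is at risk.

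**What to change.** In Tables 6 and 7 and in Section 9.7.3.4, name intrauterine clinical pregnancies after fresh or frozen transfer as the denominator and model unit for pregnancy loss. Beside the loss rate, show the number of ectopic pregnancies by cohort, from the codes already listed in Section 14.3.1, so that the excluded pregnancies are visible.

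For multiple pregnancy, either leave the denominator as it is or, if it is restricted to intrauterine pregnancies, restrict the numerator in the same way. Changing the denominator alone would create a mismatch. The definition of clinical pregnancy, and with it CPR and CCPR, can stay.

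The cost is the wording of one denominator in three places and one added table row. No new data are needed, since intrauterine pregnancy is already ascertained separately in the IVF registers. The loss analysis loses the ectopic pregnancies from its denominator, 1% to 5% under the assumptions used here.
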